This study is inspired by a recent Danish project. In this study, stem cell therapy showed clinically significant improvements on both patient-reported measures and measured the amount of saliva produced. (1) The authors suggest that the results(increased flow of saliva) may be due to a reduction of connective tissue and increased blood flow in the areas affected by radiation therapy. The authors proceed to suggest that hyperbaric oxygen treatment or other treatments attempting to increase blood flow in the radiation-affected areas could be used in combination with stem cell treatment to achieve a synergistic effect.

The hypothesis that treatment that increases the blood flow in fibrous tissue damaged after surgery or radiation has a positive effect on the tissue and its associated physiologic functions is echoed in an article about strength and shoulder mobility after breast cancer surgery(2). In the Danish national guidelines for breast cancer (3), it is also recommended that women that receive radiation therapy for their breasts because of cancer, shall receive instruction in how to treat their radiated tissue manually. The writers of the two last sources hypothesize that manual treatment of fibrous tissue damaged after surgery and radial therapy can prevent tightness in fascia and nerve tissue and preserve a proper function and mobility in shoulder and arm. The writers of the first article claims that the good results after treatment and exercises is partly attributable to the increased blood flow in the area.

A case study with 15 participants that in average 8 years previously has been through surgery or radial treatment because of cancer and who suffered from dysphagia because of fibrous tissue and neuropathy(4), showed that the symptoms dysphagia, airway problems and decreased mobility in the neck would be lowered by manual fascial techniques. The effect of any xerostomia was not monitored, but the study that reveals a new way to treat some of the other sequelae fibrous tissue in mouth and neck can cause, support my hypothesis that manual treatment of fibrous tissue caused of surgery and/or radial therapy can cause increased tissue mobility, nerve conduction, and function in the fibrous tissue.

In my project I will use the treatment protocol "Avenue of expression" (5) and a few steps from the protocol "Ten steps protocol"(6) which addresses the areas I expect to develop fibrous tissue after radial therapy and/or surgery in neck or head. The techniques used in these protocols is light (5 grams) manual craniosacral techniques, addressing the fascia in the airway system, the neck, the throat, the meninges and nerve sleeves in the cranium, the visceral cranium, and the soft tissue in the mouth. My rationale in this project is that manual treatment of scar tissue and tissue damaged by radiation will increase mobility and blood flow and therefore possibly increase the production of saliva and decrease the sense of xerostomia.

The manual treatment is combined with home exercises that targets posture in upper body and respiration. This for maintaining the effects of the manual treatment. The homeexercises is inspired by pilates and by knowledge about fascia. (7,8) the exercises are available at this link:

<https://www.[name].dk/oevelser-til-dig-der-lider-af-vejrtraekningsbesvaer-efter-kraeftbehandling/>

Outcome (changes in xerostomia) is measured by a xerostomia questionnaire inspired by the one used in "efficacy of the bioextra dry mouth care system in the treatment of radiotherapy induced xerostomia by Dirix P. Etal(9) The questionnaire used in this project was kindly lent by [name], research manager at Aarhus University Hospital, and is one they (as far as he knows) use for research on this group of patients there.

This project is a pilot project, which will hopefully lay the foundation for a larger project. I have met with [name], research manager at Aarhus University Hospital, who found the project relevant and interesting, but who needed to see more (than just one) patient cases with positive results before he would consider collaborating on a larger randomized trial. This project aims, among other things, to investigate on a slightly larger scale whether craniosacral therapy can create these positive results. If the treatment method used in this project proves to be effective, this project will be the first small steps towards:

1. a larger-scale research project, blinded and randomized and where saliva production measurement is included.
2. the development of an evidence-based and effective treatment offer for a patient group that currently lacks effective treatment offers and a treatment offer that may be able to complement stem cell therapy in the long term.

Objectives:

Main:

To examine if craniosacral therapy in chest, throat, neck, cranium and mouth , combined with specific exercises, can decrease xerostomia in people who suffer from this after radiation therapy and/or surgery in neck or mouth because of cancer in mouth or throat, by using a questionnaire "xerostomia after minimum 3 months" and comparing baseline results, with results after end of treatment and results 6 months following the last treatment.

Second

To examine if the intervention has any effect on other well-known late sequelae after treatment of cancer in mouth and neck, by asking if and how participants are experiencing these symptoms and comparing baseline results, with results after end of treatment and results 6 months following the last treatment.

Third objective

To examine, if there is any sideeffects or adverse events of the treatment

Design

This project is a pilot-study. It's a one-arm intervention study, with before and after comparisons. There is no masking(open level)

Measurement method

Main objective: The participants will fill in the Danish questionnaire named "Xerostomia questionnaire after minimum 3 months".

The questionnaire will be filled in on the treatment day, before starting the treatment, on the 5.(and last time of treatment, before starting the treatment, and as follow up, 6 month after the treatment.

The participants will be alone, completing the questionnaire.

Other monitoring

Second objective (other late sequelae)

Participants will be contacted by phone the week before starting the treatment and interviewed about, which late sequelae they are experiencing – this will be written down in their journal and will be read aloud so they can confirm. The therapist will ask then about experiencing any changes in the late sequelae mentioned before start of treatment the last time of treatment, and at 6 month following up meeting.

Participants are asked if they are experiencing following late sequelae: dry mouth, obstipation, lymphedema, tinnitus, difficulty swallowing, tense/stiff neck, problems with respiration, stiff jaw, difficulty with speaking, fatigue, difficulty sleeping and pain and mental well-being

. These late sequelae are chosen by reading results from a questionnaire about late sequelae fulfilled by members of: "Danish Network for Mouth and Throat Cancer" – a community of people who have been through treatment of cancer in throat and mouth.

Participants are also asked if they have any other late sequelae.

Third objective(side effects)

Participants are at the first treatment session receiving a diary to note if they have any side-effect after treatment. At each session the therapist will ask if the participant has been experiencing any side effects and these will be noted in the participant journal and combined together so that the results contain a total overview of experienced side effects

Intervention:

The participants will receive 50 minutes of treatment of craniosacral therapy once a week in 5 weeks. The treatment will follow the protocol "avenue of expression" and step 2c and 2c in "Ten step protocol". See appendix (1)

Statistical considerations

The participants filled in the danish questionaire " Xerostomia questionnaire after minimun 3 months". The questionnaire includes a VAS xerostomia scale 0-10 (10 is worst)

The remaining 14 questions were phrased "how much does [question subject] bother you:" (translated from Danish)

not at all (1) - a little (2) - some (3) a lot (4) very much(5)

The final question(number 15) were:

"How would you feel, if you had to live the rest of your life, with the symptoms you have now?:"
enjoyable(1), very satisfied (2) neither satisfied ore unsatisfied(3), very unsatisfied(4), terrible(5)
the sum of points from the 15 questions gives an overall score.

The remaining 14 questions were phrased "how much does [question subject] bother you:" (translated from Danish)

not at all (1) - a little (2) - some (3) a lot (4) very much(5)

The final question(number 15) were:

"How would you feel, if you had to live the rest of your life, with the symptoms you have now?:"
enjoyable(1), very satisfied (2) neither satisfied ore unsatisfied(3), very unsatisfied(4), terrible(5)
the sum of points from the 15 questions gives an overall score.

This will give two scores:

the was-scale-score between 0-10 (10 is worst)

and the score for the remaining questions between 15 – 75 (75 is best)

The questionaire will be filled in on the treatmentday, before starting the treatment, on the 5.(and last time of treatment, before starting the treatment, and as a followingup, 6 month after the treatment. The participants will be alone, completing the questionnaire.

The result will be the participants' average score from the 3 times the questionnaire is completed. Averages will be calculated omitting missing values. Unfortunately, I have not been able to find information about, how large a change in the score there is clinically relevant.

Since there is no control group, I have decided that the participants must have completed the treatment at least two years before the start of the trial to ensure that any positive effects on xerostomia and the other side effects are not simply a result of natural healing. This choice was made on the basis of a systematic review of 1366 patients(10), where it is argued that it is probably

at least after 2 years after end of cancer-treatment that a relatively static state with regard to dry mouth occurs.

Because the intervention group is so small, and heterogeneous, when it comes to age, time since treatment, gender and cancer treatment methods results should be generalised to future patient populations with great caution.

During the calculation I have received supervision, from a colleague that has a lot of experience with statistics during research.

Participants:

Inclusion criteria

- More than 18 years, able to consent to participate.
- Have finished radiation treatment and/or surgery for oro-pharyngeal head or neck cancer at least two years before enrolling the project
- They shall score at least 4 on an xerostomia numeric scale where 0 is no xerostomia.

Exclusion criteria

- Persons who by surgery have got both their submandibular saliva glands removed.

And several contraindications:— see below:

- New case of cancer within a year
- Known to have an intracranial aneurysm or 2 close family members (parents, siblings, children) known to have aneurysm or bleeding under the brain.
- Perforation of the dura within a month
- Diagnosed bulge in the medulla oblongata
- History of traumatic neck or head injury that required hospitalization
- Planning to become pregnant, or pregnant before the twelfth week at the start of the project
- Signs of active disease - must be investigated by participant's own doctor first. Sorted out in

this project:

- radiation damage to the cervical vertebrae
- If I during my journal procedure of my participant finds any signs of active disease, I will send them to their doctor and do not start my treatment before the doctors approval.

Risks, Side effects, disadvantages (long and short term)

Serious sideeffects of craniosacraltherapy is very seldom. When I was going to apply to "The central Denmark region Committees on health research ethics" for permission to carry out the project, they demanded a study of cases of serious side effects after craniosacral therapy, which made me make some extra exclusion criteria to this study. There is a single case where a person who was pregnant and had fallen had a spontaneous abortion after treatment. There are also a few cases where people who have been exposed to serious head or neck trauma have had side effects that required medical attention. Therefore, pregnancy and serious head/neck trauma are contraindicated in this project. In addition, there are a number of precautionary contraindications that are taken into account to avoid serious side effects. Read more under exclusion criteria.

Participants are instructed to contact their doctor if they experience anything concerning during the trial.

Any serious side effects will result in immediate cessation of the trial, and will of course be reported.

Commonly occurring/ not serious sideeffects

It is common for all types of patients to experience temporary fatigue, dizziness, flu symptoms, aches and pains, and increased digestive activity. It is also common to experience temporary emotional fluctuations. Since I have not treated many people with late effects of cancer, I do not know if they will have any other common late effects than the general population. Therefore it is a goal in this study to list any side-effects in this study.

Hygiene:

Since the participants belong to a group of people who are particularly vulnerable to infections and since the experiment was conducted during Covid times, face masks will be used during treatment and gloves are used when treating the mouth.

The table is disinfected between each treatment.

Gdpr

As this experiment takes place in Denmark, which is a member of the EU, there are a number of rules according to GDPR that must be observed. These are ensured in cooperation with "The central Denmark region Committees on health research ethics"

Economy:

sponsor/collaborators:

No sponsors - this study is self-financed

collaborators:

Danish Cancer Society (has made treatment rooms available

DLHM - Danish Society for Mouth and Throat Cancer (recruitment of participants)

Danish Network for Mouth and Throat Cancer (recruitment of participants)

Recruitment of participants

I have contacted various relevant hospital departments and asked if they wanted to collaborate on recruiting participants, but they have not been interested.

Participants have received information about the possibility of participating in the project through presentations held in collaboration with:

DLHM - Danish Society for Mouth and Throat Cancer

and

Danish Network for Mouth and Throat Cancer

Informed consent

The participants have signed informed consent, which is based on templates developed by "The central Denmark region Committees on health research ethics". The information has been given both orally - via oral presentations - and in writing and contains everything the research ethics committee requires. They have also signed informed written consent, where they give permission for the

publication of the results. I have been in contact with employees from "The central Denmark region Committees on health on health research ethics", to make sure that this procedure has been done properly

Insurance

In the application procedure to the "The central Denmark region Committees on health research ethics", I had to ensure that the participants in the project are covered by my medical insurance. The participants are covered by my medical insurance

Publication of results:

The results will be published on clinicaltrials.gov. I will work to have the study published in a peer-reviewed journal – also in my professional journal (Danish physiotherapists) and on Upledger International's website (the institute that trains craniosacral therapists), where they have a subpage with links to various research. If the trial has positive results, I will communicate the results orally at relevant conferences/professional days or in patient associations. I will also make the results available on my own website.

Scientific ethics section

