Appendix section

Appendix 1

Treatment protocol Xerostomi

- anamnesis and introduction to the treatment. Here I made an oral agreement with the participant that they can ask me to stop the treatment at any time. I will also ask for consent to start the treatment in another bodily area than mentioned in the protocol, if I find that it is necessary.

Physical examination:

I will examine the cranial rhythm of heels, ankles, thighs, the pelvis, the ribbs, the shoulders, in the three global cranial hand positions, and the temporal hand position with a technique intended for listening for this rhythm.

I will do an arching to find energy cysts

All findings are documented in the journal.

Treatment

In every session I will start with a stillpoint at the feet.

I'll go through the protocol as far as I can during the time available, and continue in the next session.

Diaphragm with diaphragm handgrib

- diaphragm -

- Thoracic inlet
 - with diaphragm handgrib
- Infrathyroid muscles
 - with diaphragm handgrib
- os hyoideum and retrohyoid tissue
 - with diaphragm handgrib
- c1 og c2 (1 gram technique)
- treatment of the cranium in 5 steps:
 - 1: melt in the suboccipital tissue
 - 2: platform technique
 - 3: 5 grams traction of occiput in the direction of the cranium starting from atlas
 - 4 : decompression technique of the occipital condyles
 - 5: 5 grams dural traction

Cranial treatment

- frontal lift
- parietal lift
- sphenoidal compression-decompression

- temporal unilateral og bilateral ear-pull technique
- os mandibularis compression – decompression
- os nasalis technique
- os zygomaticus og processus pterygoideus – decompression techniques
- soft-tissue-technique upper and lower lip
- os maxillaris technique
- os vomer technique
- os palatinum technique
- roof of the mouth technique
- fascial glide of suprahyoid tissue
- tongue technique
- treatment of teeths and gums
- technique for re-stabilisation :
- Os maxillaris technique– in flexion and extension
- os mandibularis technique – compression and decompression
- os sphenoidalis technique – compression and decompression
- os temporale (earpull technique)
- cranial base technique

- CV4-technique

After each session I will retest the cranial rhythms . Test results and treatment is documented in the journal.

Finish the treatment with conversation, questions etc, and with information about expected side effects of the treatment.

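### The end-of-treatment questionnaire is collected only at session 5, so anyone who stops earlier stays in the baseline average but drops out of the end-of-treatment average

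*Protocol*

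**What the plan says.** The Measurement method section places the second and third questionnaires "on the 5.(and last time of treatment, before starting the treatment, and as follow up", the latter 6 months after treatment. Statistical considerations repeats this almost word for word: "on the 5.(and last time of treatment, before starting the treatment, and as a followingup, 6 month after the treatment". For the second objective, the therapist asks about changes in "the late sequelae mentioned before start of treatment the last time of treatment, and at 6 month following up meeting". The Intervention section says "The participants will receive 50 minutes of treatment of craniosacral therapy once a week in 5 weeks", so the planned last treatment is session 5.

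The main objective rests on "comparing baseline results, with results after end of treatment and results 6 months following the last treatment". Under Statistical considerations, the result is the average score at each of the three time points, and "Averages will be calculated omitting missing values".

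Two further details matter. Participants complete the questionnaire alone, and the first sequelae interview is held by phone in the week before treatment starts. Neither instrument therefore needs a treatment session.

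**The concern.** The protocol ties the end-of-treatment score to attending the fifth session. A participant who stops after session 1, 2, 3 or 4 has a baseline form but no occasion on which the second form is handed out. An unannounced stop also misses the second sequelae interview. With missing values left out of each average, the baseline and session-5 averages then come from different sets of people.

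The design is one-arm and open, so there is no comparison group in which selective loss would show. The protocol itself calls the group small, so a few absent people can move an average. The before-after change is also meant to help decide whether a larger randomised trial is worth pursuing.

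This is a matter of what is collected. A statistical analysis plan can choose how to analyse the forms, but it cannot recover one that was never given out.

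**Working it through.** The protocol states no sample size, dropout rate, standard deviation or expected change, so there is no figure to reproduce. The check is to see who is measured when, and then what the stated averaging rule does.

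**Who is measured, as written**

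| | Baseline form | End-of-treatment form | Second sequelae interview | 6-month form |
|---|---|---|---|---|
| Completes 5 sessions | yes | yes, at session 5 | yes | yes |
| Stops after sessions 1–4 | yes | no route given | only if the last session is known to be the last | not conditional on session 5 |

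**Effect on the reported difference**

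Let *f* be the fraction stopping before session 5, *S* the stayers' baseline mean, *S + d* the stoppers' baseline mean, and *c* and *c_s* the mean changes in stayers and stoppers. On the VAS, 10 is worst, so a negative change is improvement.

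- Baseline average = (1 − f)·S + f·(S + d) = S + f·d
- Session-5 average = S + c
- Reported difference = c − f·d
- Mean change over all participants = (1 − f)·c + f·c_s
- Error = reported − all = f·(c − c_s − d)

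All values of f, d, c and c_s below are assumptions.

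1. *Nobody changes* (c = c_s = 0). The reported difference is −f·d. If stoppers start 1 to 2 VAS points worse, the apparent improvement is 0.1 to 0.2 at f = 10%, 0.2 to 0.4 at 20% and 0.3 to 0.6 at 30%. If stoppers start better by the same amounts, these become apparent worsening. On the 15–75 sum score with d = 5 to 10, the artefact is 0.5 to 1.0, 1.0 to 2.0 and 1.5 to 3.0 points in size.
2. *Equal baselines* (d = 0), c = −2, c_s = 0. The reported difference is −2.0 throughout. Over all participants it is −2 × 0.9 = −1.8, −2 × 0.8 = −1.6 and −2 × 0.7 = −1.4 at 10%, 20% and 30% stopping.
3. *Both together*, f = 20%, c = −2, c_s = 0, so the all-participant change is −1.6. With d = +1 the report is −2 − 0.2 = −2.2, too favourable by 0.6. With d = −2 it is −2 + 0.4 = −1.6, and the two parts cancel. If stoppers started still better, the sign of the error would reverse.
4. *Only participants with both forms.* This removes the f·d term but leaves f·(c − c_s), as in item 2. Pairing alone does not bring the stoppers back.
5. *Everyone completes* (f = 0). The error is zero.

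**The case against.** Several points on the other side stand.

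- A reader might infer that the results as a whole describe only those who stayed. The documents do not support that. Baseline is taken from everyone, and the third form is due 6 months after treatment. Someone who stops after session 3 still has a last treatment and so a 6-month date. The problem is confined to the end-of-treatment measurement.
- The sequelae interview is set at the last treatment, not at session 5 by number. If an early last session is announced as such, the interview could still take place.
- Appendix 1 says that "they can ask me to stop the treatment at any time". It is tempting to read this as planned withdrawal from the course. It stands in the opening talk with the participant, beside consent to work on other body areas, and most naturally concerns stopping hands-on treatment. The point does not need it, since people can leave any five-week course.
- Nothing in the protocol shows that stopping will be common. It describes the techniques as light and the expected side effects as mild and temporary.
- A reader might infer that the bias must favour the treatment. Item 3 of the working shows that it need not.
- The participant information is not at hand and may describe contact after stopping.
- The trial is a pilot with descriptive averages, and it warns against generalising.

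These limit the reach of the point and the claim about its size. They do not supply a route to an end-of-treatment score for someone who stops, and the averaging rule is fixed in the text.

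**Conclusion.** The point holds for the end-of-treatment comparison. Followed as written, the plan keeps early stoppers in the baseline average and leaves them out of the session-5 average, so the difference combines within-person change with selection.

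The likely direction is toward benefit if people with no benefit or with side effects are the ones who stop. That is general reasoning, not something the protocol shows. The assumed examples give an error of a few tenths of a VAS point at 10% to 30% stopping, with a sign that depends on how stoppers differ at baseline and in change. Neither size nor sign can be determined from the document. This is a cheap improvement to data collection, not a flaw that invalidates the trial.

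**What to change.** - Collect the end-of-treatment questionnaire and the second sequelae interview in the planned week of session 5 from every participant who had at least one session and still consents to follow-up. Use post or phone for those who have stopped.
- Keep the 6-month form at 6 months after each participant's own last treatment, and say that this applies also to those who stopped early. Counting it from the first session instead would contradict the objectives.
- Record stopping treatment separately from withdrawing from follow-up.
- At each time point, report the number with data, and give the within-participant change beside the averages.

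The cost is a few sentences in the protocol and a few posted forms or calls. The mean change may come out slightly less favourable.

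### The end-of-treatment questionnaire is completed before the fifth and last session, so it reflects at most four of the five sessions

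*Protocol*

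**What the plan says.** Four parts of the protocol bear on this point.

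- **Objectives, Main.** The effect on xerostomia is to be judged by "comparing baseline results, with results after end of treatment and results 6 months following the last treatment".
- **Measurement method.** After the form completed before the first treatment, the questionnaire is completed "on the 5.(and last time of treatment, before starting the treatment, and as follow up, 6 month after the treatment". Statistical considerations repeats the schedule almost word for word: "on the 5.(and last time of treatment, before starting the treatment, and as a followingup, 6 month after the treatment". The same section states how it is reported: "The result will be the participants' average score from the 3 times the questionnaire is completed".
- **Intervention.** "The participants will receive 50 minutes of treatment of craniosacral therapy once a week in 5 weeks".
- **Appendix 1, Treatment.** The techniques form one list, delivered in order across sessions: "I'll go through the protocol as far as I can during the time available, and continue in the next session".

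Nothing in the protocol defines the end of treatment as the moment before the last session, and no further questionnaire is scheduled between session 5 and the 6-month follow-up.

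**The concern.** The objective promises a score taken once the course is finished. The schedule delivers a score taken while one session is still to come. This is not a detail that an analysis plan could settle later, because a measurement that was never taken cannot be recovered.

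Two readings of the results are at stake. The first is the change from baseline to the end of treatment: as scheduled, it is a four-session change carrying a five-session label. The second is persistence. The introduction gives the home exercises the purpose of preserving what the manual treatment achieves, and three averages reported side by side invite the reader to compare the second with the third. Any benefit from session 5 would be missing from the second average and present in the third. The immediate effect would then look smaller than it was, and its durability better than it was.

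The study has no control group and only two post-baseline time points, and its results are meant to help make the case for a larger randomised trial. A reader planning that trial needs to know how much treatment each average follows.

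**Working it through.** The protocol states no sample size, power or expected effect for this point, so there is no figure of its own to reproduce. The check sets the schedule against the objective, counts sessions, and then shows what the mismatch could do.

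**1. Timeline, taking the first session as week 0** (Intervention; Measurement method)

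| Week | Event | Sessions completed before the form |
|---|---|---|
| 0 | Form 1, then session 1 | 0 |
| 1, 2, 3 | Sessions 2, 3, 4 | no form |
| 4 | Form 2, then session 5 | 4 |
| 6 months after treatment | Form 3 | 5 |

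**2. Treatment delivered before form 2**

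- Sessions: 5 − 1 = 4 of 5.
- Scheduled minutes: 4 × 50 = 200 of 5 × 50 = 250, and 200 / 250 = 0.80.

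Form 3 follows all 250 minutes.

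**3. Effect on the first comparison**

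Let E be the improvement in VAS points after the full course and s the share of E that session 5 adds. The protocol gives neither, so both are assumptions. The improvement seen at form 2 is E × (1 − s). With E = 2.0:

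| s | Improvement at form 2 | Shortfall, E × s |
|---|---|---|
| 0 | 2.0 | 0 |
| 0.1 | 1.8 | 0.2 |
| 0.2 | 1.6 | 0.4 |
| 0.3 | 1.4 | 0.6 |

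**4. Effect on the reading of persistence**

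Let L be the share of E lost by 6 months, also an assumption.

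- Improvement at form 3: E × (1 − L).
- Apparent change from form 2 to form 3: E × (1 − L) − E × (1 − s) = E × (s − L).
- True change from the end of the course to form 3: −E × L.
- Difference between apparent and true: E × s.

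With E = 2.0 and s = 0.2 (positive values are further improvement):

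| L | Improvement at form 3 | Apparent change, form 2 to 3 | True change since end of course |
|---|---|---|---|
| 0 | 2.0 | +0.4 | 0 |
| 0.1 | 1.8 | +0.2 | −0.2 |
| 0.2 | 1.6 | 0 | −0.4 |
| 0.3 | 1.4 | −0.2 | −0.6 |

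In every row the apparent change is 0.4 points more favourable than the true one. At s = 0 the two agree.

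**The case against.** The timing mismatch itself is hard to dispute. The case on the other side is about how much it matters.

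- **No comparison of the second and third scores is planned.** The objective compares each later score with baseline, and persistence is not an endpoint. This is correct, and it makes the persistence problem one of interpretation. It leaves the first comparison, which is planned and is mislabelled.
- **The size rests on assumed values.** This stands. The protocol has no dose-response information, so the magnitude and even the direction of the distortion are unknown. The text alone supports only the count of four sessions out of five.
- **Eighty percent of the minutes is not 80% of the intervention.** This also stands. Home exercises are part of the intervention and are not counted in those minutes, and they could contribute to change after form 2. Appendix 1 also lists history-taking, examination and retesting without saying whether they use part of the 50 minutes.
- **Any error in the first comparison is conservative.** If session 5 helps, the early effect is understated, not inflated. True, but the same omission flatters durability.
- **Completing the form before a session is sensible.** It avoids the short-lived reactions the protocol expects after treatment, and it secures the form at a visit. The protocol does not give this reason, but it is a good one. A form one week after session 5 keeps the first advantage and gives up the second.
- **This is a small, open pilot whose timing is stated openly, and parts of the text suggest the data are already collected.** These points bear on which remedy is still available. They do not make the objective and the schedule agree.

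**Conclusion.** The concern holds. As written, the protocol would report a score taken after at most four of five sessions (200 of 250 scheduled minutes) as the end-of-treatment result. That follows directly from the text and needs no assumption.

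The consequence in points depends on E, s and L, none of which the protocol gives. With a full-course improvement of 2.0 VAS points and s between 0 and 0.3, the end-of-treatment improvement is understated by 0 to 0.6 points, and a reading of persistence is flattered by the same amount. This assumes that session 5 does not make symptoms worse and that the home exercises produce no separate change after form 2.

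The comparison of baseline with 6 months follows the full course and is sound in this respect. The fault is limited to the first comparison and to any conclusion about maintenance. It should be corrected, and it does not undermine the study as a whole.

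**What to change.** **If data collection is still open.** Move the second questionnaire to one week after session 5, the same gap it now has after session 4. Hand out the form and a return envelope at session 5. Participants complete it alone at home and post it back. Change the timing in both Measurement method and Statistical considerations.

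The cost is one form and one envelope per participant plus a reminder call, with no extra visit and no change in treatment. The drawback is that some forms may not come back. The group is small and averages are taken over available values only, so the reminder call matters.

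**If the forms have already been collected as scheduled.** Only wording needs to change:

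- Report the second average as the score before session 5, after four of five sessions.
- Amend the first comparison in the main objective to match.
- Present the 6-month score as the only result after the full course.
- Do not describe the change from the second to the third questionnaire as maintenance of the full-course effect.
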